## Specific aims are as follows:

**Aim 1**: Compare the clinical effectiveness of 3 different BPSPs on pumped milk volume during Days 8-15 postpartum.

**Aim 2:** Compare lactation outcomes for the three groups, including 1) maintenance of SA through to postpartum day 14-15, 2) rate of increase in daily pumped MOM volume, 3) whether or not mothers achieve CTV by day 14-15 postpartum, 4) cumulative pumped MOM volume over days 1-7 and 8-15) MOM removal efficiency, and 5) lactation duration.

Aim 3: Compare maternal perceptions of comfort, effectiveness, efficiency, and convenience of the 3 BPSPs.

**Aim 4:** Compare infant outcomes for the including: 1) proportion of feedings consisting of MOM during the NICU hospitalization, 2) proportion discharged consuming any MOM, and 3) proportion receiving MOM at 3 and 6 months of life.

**Exploratory Aim 1**: Explore potential benefits of the 3 BPSP on lactation outcomes of mothers with comorbidities known to negatively affect lactation outcomes (high BMI/obesity, diabetes, pregnancy induced hypertension).

**Exploratory Aim 2**: Explore whether mothers categorized as having faltering lactation on postpartum day 6-8 and who use BPSP1, BPSP2, or Symphony Plus BPSP (Standard Care) achieve the same lactation outcomes (Aims 1, 2, 4) as do mothers who do not demonstrate faltering lactation at postpartum day 6-8.

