The NICU at UF Shands admits infants that are racially diverse regardless of private or Medicaid insurance coverage. All mom that meets the above criteria would be eligible for enrollment. Informed consent will be obtained by mothers in their postpartum hospital room or in the NICU while visiting their infant prior to 48 hours postpartum. The informed consent includes mother's permission to access their infant's chart to collect information up until infant's discharge. The infant has no study interventions. In the rare instance that an infant breastfeeds, intake will be determined through test weighting (infant weight pre and post breastfeeding). Prior to the mother's hospital discharge, she will be provided an empty payment card where participants will receive compensation, by adding payments for completing study events, listed below. After enrollment, a 2-minute maternal interview will be used to collect information to determine pre-pregnancy BMI and other factors that might impact lactation success (Appendix B). Information will be collected related to pumping frequency and pumped milk volume prior to enrollment (Appendix I). All enrolled mothers will be provided breast pumping instructions to optimize their pumping behaviors prior to achievement of secretory activation. This 30-minute optimization session will be provided by a Research Nurse Coordinators, who is also an International Board-Certified Lactation Consultant (IBCLC). The instructions will be standardized using a score card, which provides prompts for education discussion and video links about pumping practices, breast and nipple assessment, breast shield sizing and comfort. (Appendix F). A daily sample of 0.3 mL of pumped MOM (if mother has pumped at least 5mL/day) will be tested for MOM sodium level as an indicator of secretory activation. At day 6-8 postpartum, mothers at high risk of suboptimal lactation will be identified and randomized to one of three BPSPs Mothers will be determined to be at risk if they have (1) achieved secretory activation (change from small volumes of colostrum to large volumes of more mature milk; determined by a milk sodium level < 20 mM) and (2) have a pumped milk volume < 350 mL/d. Mothers who are identified as being not at risk for suboptimal lactation (have achieved secretory activation and their pumped milk volume is > 350mL/d) will not be randomized but will continue with standard care regarding BPSPs, and continue to have data regarding lactation collected. Mothers who do not reach SA, determined by a milk sodium level > 20 mM, will be withdrawn from the study and referred to the UF Shands Lactation Team. All mothers that achieve SA, will be provided a second 30-minute standardized breast pumping optimization session with instructions by a Research Nurse Coordinator who is an IBCLCs at day 6-8 postpartum. Mothers will complete the Maternal Perceptions Survey (Appendix K/Part A only) before starting new pattern. If randomized, Moms will complete the Maternal Perception Survey (Part A/B) on Day 9-11. A score card, designed for mothers who have already achieved secretory activation, includes educational prompts and video links regarding milk volume, pumping behaviors, breast and nipple assessment, flange fit and comfort will be utilized. (Appendix G). Should a mother be unable to obtain transportation to the NICU, they will be provided transportation through Uber Health, provided they live within a 60-mile radius of UF Shands due to cost limitation of study.

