
Mothers will be provided a payment card for amount listed following completion of the listed study event(s).

- 1. All mothers enrolled: optimization pumping session with the study Research Nurse Coordinator IBCLC, completion of the first MAACL, maternal interview, and lactation experience questionnaire. (\$25.00)
- 2. All mothers that achieve SA: Following completion of the second pumping optimization session with the study Research Nurse Coordinator IBCLC and completion of Maternal Perceptions Survey (Part A only) (\$25.00)
- 3. All mothers that do not reach SA, will be withdrawn from the study and not eligible for further compensation.

4. Following completion of the second MAACL, lactation experiences survey, maternal perception survey (if randomized) and return of all "loaned" breast pumps (\$50.00)

Total Compensation: Moms withdrawn at Week 1 (did not reach SA) \$25.00. All other moms (reaching SA) will receive up to (\$100)

**Sample Size Determination:** With 30 dyads (mom and infants) will randomized, using the block method, to each intervention group (2 alternate, one standard care), assuming a = 0.02 (Type I error rate), two-sided; independent sample t-test comparison of means (adjusted for multiple comparison between 3 groups); equality of variance between groups with 30 mothers per group we will have 80% power to detect a difference of 300 ml (effect size of 0.84; sd=350.0) between the groups.

**Randomization:** Those mothers who have been identified as being at high risk for suboptimal lactation will be randomly assigned using Block randomization to use one of three different BPSPs [BPSP1, BPSP2, or Symphony Plus BPSP (Standard Care)] for 7 days.

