**Aim 3:** Will compare maternal perceptions of comfort, effectiveness, efficiency, and convenience of the 3 different breast pump patterns.

Mother's perception regarding the comfort, rhythm, effectiveness, and ease of use of the three BPSPs will be assessed via a text message hyperlinked Qualtrics survey within 7 days of study completion. A reminder will be sent if no response in 7 days (Appendix K).

**Aim 4:** A fourth aim will compare proportion of feedings consisting of MOM consumed by infants between the 3 groups. Daily proportion of total feeds consisting of MOM consumed during the first 15 days and proportion of total feeds consisting of MOM consumed during the 24 hours prior to discharge will be recorded from the infant's EMR. Proportion of feeds that include MOM after discharge will be determined until the mother ceases lactation or the infant is 6 months old through monthly text message hyperlinked surveys through Qualtrics asking the total number of feeds in the past 24-hours that consisted of MOM (either direct breastfeeding or feeding expressed MOM).

**Exploratory Aim 1**: Will explore potential benefits of the three BPSPs on the lactation outcomes in Aim 1 and 2 of mothers with co-morbidities known to negatively affect lactation outcomes (high BMI/obesity, diabetes, pregnancy induced hypertension).  A subset of mothers diagnosed with high BMI/obesity, diabetes, and/or pregnancy induced hypertension will be classified as having 1, 2, or 3 risk factors known to negatively affect lactation outcomes. Potential benefits of the three BPSPs will be explored in this subset of mothers.

Exploratory Aim 2: Explore whether mothers identified as having faltering lactation who use an alternate BPSP (BPSP 1 or 2) achieve the same lactation success as mothers identified as not having faltering lactation (pumped MOM volume  $\geq 350$  mL/d by day 6-8). Lactation outcomes (see Aim 1 and 2) will be compared between mothers who were randomized to use either BPSP 1 or 2 and those mothers who were not randomized because they were not identified as having faltering lactation.

Confounding Variables. The following variables may affect pumped MOM volume in mothers of critically ill infants. While control of these variables within the study is impossible, we will carefully document these factors on all enrolled mothers to allow for inclusion in statistical analysis as adjustment variables. See **Table 1** for additional confounding variables.

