3. Duration of partial or exclusive MOM feedings after discharge	Monthly maternal text message with hyperlinked surveys through Qualtrics. (App J)	Monthly until lactation cessation or infant is 6 months of age.					
Length of NICU hospital stay; infant nutritional, and health outcomes	Days infant remained hospitalized in the NICU, nutritional and health outcomes	From birth until discharge.					
Covariates (1-6) below							
1. Demographic data	Maternal: Race/Ethnicity, delivery of > one infant, delivery mode, parity, BMI, co-morbidities. Infant : Gestational age at birth, birthweight, Apgar score. % of type of feeding consumed (MOM, donor human milk, formula). (App A, App N)	Upon entry into study and during the 15-day study period					
2. Number of pumping sessions per day	# of times a mother pumps her breasts per day. (App L)	Daily for 15 days					
3. Skin-to-skin care	Total minutes and episodes of skin-to-skin care.	Daily for 15 days.					

4. Maternal mood	Results of 2 MAACL-R tests completed by mom.	Prior to her hospital discharge and at 15					
	(App D)	days postpartum.					
5. Lactation experience	(a) Feeding plan prior to delivery, previous experience	Before maternal hospital discharge (a)					
	with breastfeeding and/or pumping, lactation intent, home	At end of study (b)					
	pump status (b) Lactation intent, lactation goals lactation						
	consultations, galactagogues, mastitis diagnosis and						
	treatment, use of hormonal birth control, home pump status						
	(App C)						

Table 2: Timeline of events over the 15-day study

Measure	0*	1	2	3	4	5	6	7	8	9	10	11	12	13	14	15
Consent, maternal interview		Х-	-X													
Pumping optimization		X-		-X			X-		-X							
MOM NA/K Level		Х-														- X
Lactation risk assessment							X-		-X							
Randomization							X-		-X							
Determination of CTV																X
Measures of pumped milk volume		X	X	X	X	X	X	X	X	X	X	X	X	X	X	X
Measures of infant consumption of MOM		X	X	X	X	X	X	X	X	X	X	X	X	X	X	X
Maternal perception survey (Part A)							Х-		-X							
Maternal perception survey (Part A/B)										Х-		-X				
MACCL			Х-	-X												X
Lactation experiences			X													X

\* = day of birth

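### Aim 4 names the MOM share over the NICU stay, but the schedule covers only days 1-15 and the last 24 hours, and the 15-day window is not limited to days after randomisation

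*Protocol*

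**What the plan says.** - **Named outcome.** Protocol Section 5, Aim 4, item 1: "proportion of feedings consisting of MOM during the NICU hospitalization". MOM at discharge and at 3 and 6 months are separate items of the same aim.
- **Scheduled measurement.** Protocol Section 6, Research Procedures and Analyses, Aim 4: "Daily proportion of total feeds consisting of MOM consumed during the first 15 days". The second in-hospital measure is the MOM share of feeds over the last day before the infant goes home. Both are taken from the infant's medical record. The paragraph opens by announcing a comparison between the three groups. Table 1 repeats the two windows, and Table 2 marks infant MOM consumption on days 1 to 15.
- **Start of the intervention.** Sample and Setting: "At day 6-8 postpartum, mothers at high risk of suboptimal lactation will be identified and randomized to one of three BPSPs". The Randomization paragraph gives the duration: "BPSP1, BPSP2, or Symphony Plus BPSP (Standard Care)] for 7 days".
- **Windows used for other outcomes.** Aim 1: "Compare the clinical effectiveness of 3 different BPSPs on pumped milk volume during Days 8-15 postpartum". Milk removal efficiency also uses days 8-15, and cumulative volume is split into days 1-7 and 8-15.
- **A general row in Table 1** runs from birth to discharge: "Days infant remained hospitalized in the NICU, nutritional and health outcomes". It does not name the MOM share.

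**The concern.** There are two separate problems in one outcome.

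First, the aim and the schedule describe different quantities. The aim covers the whole NICU stay. The schedule covers the first 15 days and the final 24 hours, with nothing planned in between for longer stays. The MOM share at discharge does not fill that gap, because it is a single-day measure and Section 5 already lists MOM at discharge as its own item.

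Second, the 15-day window straddles randomisation and is not divided. Feeding before the assigned pattern starts cannot differ between arms because of the pattern. A comparison that includes those days would pull the difference towards zero and let chance imbalance from before randomisation into the result.

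As written, a reader cannot tell whether the planned Aim 4 result is a 15-day, a post-randomisation or a whole-stay comparison, and that choice could end up being made after the data are seen.

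**Working it through.** **1. The protocol's own figures.** No effect size, SD or power is given for Aim 4, so there is no Aim 4 figure to reproduce. The only power statement concerns pumped volume: 30 per arm, "assuming a = 0.02 (Type I error rate), two-sided", effect size 0.84, 80% power. A noncentral t calculation gives 80.3%, so that statement reproduces. It does not bear on Aim 4.

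**2. Coverage of the stay.**
- Stay of 15 days or less: the daily record covers all of it.
- Longer stay: day 16 up to the last 24 hours before discharge is not scheduled for this outcome.
- The protocol gives no length of stay, so the size of this gap cannot be computed. Longer stays are foreseeable, because mothers must be expected to be pump-dependent for at least 14 days.

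**3. Share of the 15-day window before randomisation.** Randomisation falls on day 6, 7 or 8, and the day itself can be counted as before or after.
- Fewest pre-randomisation days: day 6, counted as after. 5 days, 5/15 = 33%.
- Most: day 8, counted as before. 8 days, 8/15 = 53%.
- Day 7: 6/15 = 40% or 7/15 = 47%.

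**4. Effect on a pooled comparison.** Assume that the 15 daily values are averaged with equal weight and that the effect is constant from the start to day 15. The expected difference is then multiplied by (15 − pre)/15:
- pre = 5: 10/15 = 0.67
- pre = 6: 9/15 = 0.60
- pre = 7: 8/15 = 0.53
- pre = 8: 7/15 = 0.47

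For a mother who starts on day 6, seven days of use end on day 12 or 13, so a constant effect to day 15 also assumes that the effect persists after use.

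**5. What this could mean for power (illustration only).** None of these inputs is stated for Aim 4: a post-randomisation effect of 0.84 SD, borrowed from the volume calculation; 30 per arm; alpha 0.02; and an equal day-to-day correlation ρ of 0.3 to 0.9. The variance of an m-day mean is proportional to V(m) = [1 + (m − 1)ρ]/m, so the standardised effect on the 15-day mean is

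0.84 × (post/15) × √(V(post)/V(15)), with post = 15 − pre.

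- Most favourable case: ρ = 0.3, pre = 5 gives 0.579 and power 44.5%.
- Least favourable case: ρ = 0.9, pre = 8 gives 0.394 and power 20.1%.

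On post-randomisation days alone the power under these assumptions is about 80%. On an unadjusted 15-day mean it is about 20% to 45%.

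**The case against.** The strongest reply is that the Aim 4 paragraph describes data capture, not analysis. It says which daily values are recorded. Nowhere does the protocol say that the 15 values are averaged and compared between arms, and how daily values are summarised is commonly left to a statistical analysis plan, which is not at hand. This stands. A reader might infer that the plan does dilute the arm difference; the protocol does not support that, because comparing only post-randomisation days would involve no dilution at all.

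The early days also have a use. Exploratory Aim 2, as listed in Section 5, applies the Aim 4 outcomes to mothers who are never randomised, and Table 1 lists the percentage of each feeding type as a covariate over the 15-day period. That explains why days 1-7 are recorded. It does not say which days form the between-arm outcome, and the covariate row is not limited to pre-randomisation days either.

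A reader might also infer that the in-hospital outcome is not obtained at all. That goes too far. The record is complete for stays of up to 15 days, the 24-hour measure before discharge falls after randomisation for any infant discharged more than a day after it, and consent allows chart access until discharge. What remains is that the schedule does not name the MOM share between day 15 and the last 24 hours. The general nutritional row in Table 1 does not cure this.

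**Conclusion.** The point holds in two limited parts.

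- **Inconsistent outcome.** Section 5 and the Aim 4 procedures define different quantities. For infants who stay beyond day 15, the named one cannot be computed from the scheduled data. How many infants this affects is unknown, since no length of stay is given.
- **Undivided window.** Between 33% and 53% of the 15 days precede any possible effect of the pattern. To call this about half the window would describe only the upper part of that range. The shrinkage to 47% to 67% depends on equal-weight pooling and a constant effect after the start, neither of which the protocol states. The power figures rest on further borrowed assumptions and correct no stated claim.

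Aim 4 is not the primary aim. Aim 1 has its own window of days 8-15, and its result is unaffected. The change is worth making because it is cheap and settles the outcome before the data are seen.

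**What to change.** 1. Define the Aim 4 in-hospital between-arm outcome as the mean daily MOM proportion from the day after pattern start to day 15, or to discharge if earlier, adjusted for the mean daily proportion before randomisation.
2. Report the MOM share in the 24 hours before discharge as a separate outcome.
3. Reconcile Section 5 with the Aim 4 procedures and Tables 1 and 2. Either name the two measures above in place of the whole hospitalisation, or keep the whole stay and extend the scheduled chart extraction of the MOM share to discharge.

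**Cost.** Items 1 and 2 use values that are already collected and need only wording. For item 3, the first option gives up any claim about the whole stay. The second keeps that claim at the price of more chart extraction, which the consent described in Sample and Setting already allows.

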vials of MOM brought to the NICU and place the sample onto the sensor of an ion selective electrode analyzer (HORIBA, Japan) which is a hand-held machine used for sodium and potassium analysis (see photo), has been validated for accurate analysis of human milk sodium and potassium levels, and will be calibrated prior to every analysis. Although both sodium and potassium are secreted into milk via transcellular pathways, sodium but not potassium is also transferred from the maternal circulation via patent paracellular pathways. Thus, it has been suggested that a milk sodium to potassium ratio would standardize sodium level for individual women. While no differences have been reported between the ability of sodium alone versus a Na:K ratio to predict pumped milk volume, we will also measure potassium levels. (Appendix H) To ensure accuracy, individuals performing sodium analysis will be trained and evaluated prior to beginning analysis and quarterly. Our team is highly skilled in milk collection, processing and analysis.

Rate of increase in daily pumped MOM volume, achievement of secretory activation (Yes/No), and cumulative MOM volume over days 1-7 and 8-15 postpartum. MOM volume will be measured as discussed in Aim 1 and each of the outcomes determined.

Milk removal efficiency. Efficiency of milk removal will be determined by mls of MOM pumped per minute of pumping (cumulative per day and cumulative over days 8-15). Minutes of pumping is measured and recorded on the SMART pump (Appendix M).

Lactation Duration. Number of days a mother lactates (either via breastfeeding or expressing MOM) during her infant's hospitalization and whether or not she is lactating at infant discharge will be collected. Mothers will be determined to have ceased lactation when they are no longer bringing MOM to the NICU, are not placing the infant to breast for nutritive or non-nutritive sucking, and states they are no longer lactating when questioned. If still lactating at their infant's NICU discharge, mothers in all groups will be questioned regarding their continued lactation through monthly text message hyperlinked surveys via the Qualtrics platform until their infant is 6 months of age or she has ceased lactation. If a mother ceased lactation within the past month, she will be asked the week within the past month she discontinued lactating (Appendix J).

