Skin-to-skin care: Episodes and duration of skin-to-skin care (holding infants dressed in a diaper on their mother's bare chest) will be documented by bedside nurses and data collected from the infant's EMR. Skin to skin care has been associated with increased MOM production in observational studies,  yet the frequency or duration needed is not known, and skin-to-skin care may not be possible due to an infant's critical status.  Skin-to-skin care is encouraged in this NICU and nursing protocols are in place to provide support to all mothers. When stable and of appropriate maturity, infants too immature to orally feed are encouraged to suckle at an empty breast during skin-to-skin care and the number and duration of these episodes will be collected.

Lactation Support: Episodes of lactation support will be documented by lactation consultants in the infant's EMR. Although lactation support may improve breastfeeding success, limited data exists regarding the effect of lactation support in pump dependent mothers of critically ill infants. There are 5 (3 FTE) lactation specialists providing services to mothers in the hospital and who evaluate all mothers prior to discharge and provide ongoing services to mothers whose infants remain in the NICU which is congruent with all mothers expressing MOM for infants in the NICU. Information regarding any lactation support mothers receive outside of UF Health will be determined through monthly surveys. If no response within 7 days, a one-time reminder will be sent (Appendix C; Appendix J).

Maternal Mood. Maternal mood affects breastfeeding success in healthy term infants and may impact lactation success in mothers of critically ill infants. Prior to hospital discharge, and at 15 days postpartum, all mothers will be asked to complete the MAACL-R; a standardized instrument with well-documented psychometric properties that assesses mood states by using positive and negative mood state scales for Anxiety, Depression, Hostility, Positive Affect and Sensation Seeking. It consists of 132 adjectives at  $\leq$  an  $8^{th}$  grade reading level,

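### The post-discharge outcome is a proportion of feeds, but the survey item described for it collects only the count of MOM feeds, with no total to divide by

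*Protocol*

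**What the plan says.** The Aim 4 paragraph of the protocol's Research Procedures and Analyses by Specific Aim defines the outcome: "Proportion of feeds that include MOM after discharge will be determined until the mother ceases lactation or the infant is 6 months old". The source is a monthly text-message survey, described as "asking the total number of feeds in the past 24-hours that consisted of MOM". The bracket that follows, "either direct breastfeeding or feeding expressed MOM", says which routes of feeding count as MOM.

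The same paragraph treats the hospital stay differently. Both the daily figure over the first 15 days and the figure for the 24 hours before discharge are shares of total feeds taken from the infant's medical record.

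Table 1 lists a further item from the monthly survey, "Duration of partial or exclusive MOM feedings after discharge", and cites Appendix J as the instrument. The Lactation Duration paragraph under Aim 2 adds that the survey asks about continued lactation and, if it has stopped, the week it stopped. The Lactation Support paragraph adds: "Information regarding any lactation support mothers receive outside of UF Health will be determined through monthly surveys".

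In Section 5 (Specific Aims), Aim 4 has one post-discharge item, the third: the proportion receiving MOM at 3 and 6 months.

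**The concern.** The Aim 4 sentence names a ratio and then describes collecting only its numerator. In hospital the medical record can supply the denominator. After discharge the survey is the only source the protocol describes.

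The question is a 24-hour recall put to the mother once a month. A total not asked for at the time cannot be recovered later, and no analysis plan can supply it. Assuming a constant number of feeds would be a poor substitute, because totals may differ between infants and change with age.

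At stake is the feed-level comparison of the three suction patterns after discharge and, on one reading of Table 1, the split between exclusive and partial MOM feeding.

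**Working it through.** The protocol gives no figure to reproduce here. The check is whether each outcome can be derived from the item as described.

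**Notation.** Over the past 24 hours, let *m* be the number of MOM feeds and *T* the number of feeds of any type. The item as described yields *m*.

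**1. Post-discharge proportion of feeds (Aim 4 paragraph).** Proportion = *m*/*T*. *T* is not described as collected. The protocol gives no number of feeds per day, so take *T* from 6 to 12 as an assumption, with a reply of *m* = 6:

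| Assumed *T* | *m*/*T* |
|---|---|
| 6 | 6/6 = 100% |
| 8 | 6/8 = 75% |
| 10 | 6/10 = 60% |
| 12 | 6/12 = 50% |

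One reply is therefore compatible with anything from half to all feeds. The exception is *m* = 0, which gives 0% for any *T* above zero.

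**2. Exclusive or partial MOM feeding (Table 1, if the split is intended).** Exclusive feeding requires *m* = *T* with nothing else given. In the table above, the same reply is exclusive in the first row and partial in the other three.

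**3. Receipt of MOM at 3 and 6 months (Section 5, Aim 4 item 3).** Read as any MOM, this is yes if *m* > 0 and no if *m* = 0. *T* is not needed.

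**4. In-hospital proportions.** These are stated as shares of total feeds from the medical record. They do not use the survey.

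**5. Other survey content.** Continued lactation, week of cessation and outside lactation support are the other topics described. None of them supplies *T*.

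**6. Mixed feeds.** The outcome is worded "Proportion of feeds that include MOM after discharge will be determined", whereas the question counts feeds that consisted of MOM. If *x* feeds in the day combine MOM with something else and *a* feeds are MOM alone, the outcome as worded gives (*a* + *x*)/*T* and the question as worded gives *a*/*T*. They differ by *x*/*T*, so the numerator also needs one definition.

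**The case against.** The strongest objection is that the instrument cannot be seen. Appendix J is cited but not shown, and the Aim 4 sentence is a one-clause summary. It omits the questions on cessation and on lactation support, so it is plainly not a full list of the survey's items. Its silence on total feeds does not show that the question is missing. This stands, and it limits the point to the survey as the protocol describes it. It does not repair the text: none of the other described topics gives a denominator, and if Appendix J does ask for total feeds, the Aim 4 sentence describes its own measure incompletely.

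A reader might infer that the whole post-discharge part of Aim 4 is lost. The protocol does not support that. The only post-discharge item listed under Aim 4 in Section 5 needs no more than a count above zero, which the described question gives.

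A reader might also take Table 1 to require separate exclusive and partial durations. Its wording joins the two with *or*, and its timing runs to cessation of lactation or 6 months. It can fairly be read as the duration of any MOM feeding, for which no denominator is needed. That part of the point is therefore conditional.

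Finally, the 6-to-12 range is only an illustration. It shows that the ratio is undetermined and measures no effect on any comparison in the trial. That is accepted.

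**Conclusion.** The point holds in limited form. As the protocol describes the survey, the post-discharge proportion of feeds cannot be derived unless the MOM count is zero. Exclusive feeding cannot be told from partial feeding if Table 1 intends that split. With assumed totals of 6 to 12 feeds, a single reply of 6 spans 50% to 100%.

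The protocol does not establish that the survey actually used has this gap, because Appendix J is not shown. The primary outcome, the sample size, the in-hospital proportions and Aim 4 item 3 are untouched. This is a minor point on one secondary, feed-level measure. It is worth settling before data are collected because the loss would be permanent.

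**What to change.** In the Aim 4 paragraph and in the monthly survey, ask for two numbers for the past 24 hours: total feeds of any type, and feeds that included MOM. Compute the proportion from the pair.

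Use one wording for mixed feeds in both the outcome and the question, and say how such feeds are counted. If exclusive and partial status are wanted from Table 1, state the rule. A count that admits mixed feeds can equal the total without feeding being exclusive, so the rule has to deal with that case. If only the duration of any MOM feeding is meant, say so in Table 1.

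If Appendix J already asks for total feeds, no change to the survey is needed for the proportion, and the Aim 4 sentence should be corrected to say so.

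The cost is one extra question in an existing text-message survey, or one clause of protocol text.
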